#### **4.6.5.1. Potentially Clinically Significant Laboratory Values**

Criteria for determining values of laboratory tests that are considered potentially clinically significant (PCS) are listed in [Appendix C](#) of this SAP. The number (%) of subjects with post-baseline PCS values who did not have PCS values at baseline will be presented for each laboratory parameter with PCS criteria. Results from unscheduled visits will be included in identification of subjects with post-baseline PCS values, as applicable. For the calculation of the percentages of subjects, the denominator will be based on the number of subjects who had no PCS values at baseline and had at least one post-baseline assessment for the specific laboratory parameter of interest. The numerator will be based on the number of subjects from the denominator who had at least one PCS value post-baseline for the specific laboratory parameter of interest.

A listing of subjects with any PCS laboratory values will be provided.

#### **4.6.5.2. Hypercalcemia**

A hypercalcemic event (hypercalcemia) is defined as an elevated serum calcium (albumin-corrected) value  $\geq 0.3$  mg/dL (or  $\geq 0.08$  mmol/L) above the upper limit of the normal range (ULN).

Three cutoff levels of serum calcium (albumin-corrected) values will be defined:

- a.  $\geq$  ULN
- b.  $\geq$  ULN + 0.3 mg/dL (or  $\geq$  ULN + 0.08 mmol/L)
- c.  $\geq$  ULN + 1.0 mg/dL (or  $>$  ULN + 0.25 mmol/L)

The following summaries and analyses will be provided by treatment group for each of the cutoff levels above:

- Number (%) of subjects with at least one occurrence of a serum calcium (albumin-corrected) value above the cutoff level at each visit, timepoint, and overall (entire treatment period):
  - The corresponding 95% CI based on Wilson's Score method will be provided per treatment group.
  - For the number of subjects with at least one occurrence of a serum calcium (albumin-corrected) value above the cutoff level during the entire treatment period:
    - The treatment groups will be compared using the chi-square test.
    - The risk reduction between the treatment groups (calculated as Abaloparatide-sMTS – Abaloparatide-SC) will be provided together with the 95% CI based on Newcombe's method.
    - The relative risk reduction between the treatment groups (calculated as (Abaloparatide-sMTS – Abaloparatide-SC)/Abaloparatide-SC) will be provided together with the 95% CI based on Wald's method.
- Number of occurrences of a serum calcium (albumin-corrected) value above the cutoff level per subject during the entire treatment period
- The ratio of the total number of occurrences of a serum calcium (albumin-corrected) value above the cutoff level to the total number of serum calcium (albumin-corrected) blood samples per subject during the entire treatment period.

Mean ( $\pm$ SE) serum calcium (albumin-corrected) values will be plotted over study visit by treatment group. All serum calcium (albumin-corrected) results will be included in the plot, which will indicate the results at pre-dose and 4-hours post-dose at each visit, as applicable.

To evaluate the relationship between age and hypercalcemia, the number (%) of subjects with at least one occurrence of hypercalcemia at each visit and overall (entire treatment period) will be summarized by treatment group and age group (< 65, 65 - < 75, and  $\geq$  75 years).

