#### **1.2.5.2. Safety and Tolerability Endpoints**

Safety and tolerability evaluations will be based on treatment-emergent adverse events (TEAE), including AEs of special interest (AESI), vital signs (orthostatic blood pressure, heart rate, body temperature, and respiration rate), electrocardiograms (ECGs), laboratory tests (serum chemistry, hematology, coagulation, and urinalysis), investigator assessment of local tolerance, subject assessment of local tolerance, and presence of anti-drug antibodies.

In addition, the presence of hypercalcemia and of hypercalciuria based on laboratory values will be assessed.

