#### **4.6.5.      Laboratory Data**

Clinical laboratory values will be provided in conventional units and in standard international (SI) units by the central laboratory, unless otherwise specified.

In this study, local labs were allowed for screening. In addition, the original central lab was [REDACTED] Midway through the study, [REDACTED] was replaced with Medpace. Normal values of laboratory parameters in this study were provided by different local and central laboratories with inconsistent units and normal ranges. Thus, all numerical values will be converted to SI units and normalized to a standard set of reference/normal ranges as described by Chuang-Stein (1992 and 2001). The normalization process will be performed separately for each of the laboratory parameters as described in [Appendix D](#), using the Medpace normal ranges as the reference ranges.

Summaries of laboratory data will be presented using normalized laboratory values. Summaries using descriptive statistics by treatment group and study visit will be presented based on the SI units, including absolute results and changes from baseline. This includes serum chemistry, hematology, coagulation, urinalysis (for quantitative urinalysis assays), hormones and Vitamin D. In the event of repeat assessments, the last non-missing value per study day/time will be used in the summary statistics. Results from unscheduled visits will not be included in the descriptive summary tables.

Tables for the shift of laboratory data from baseline to the worst post-baseline value and from baseline to Month 12 (Visit 16) will be presented by treatment group. Results for serum chemistry, hematology, coagulation, and urinalysis will be presented by category (above normal limit, within normal limit, below normal limit). For shift tables from baseline to worst post-baseline value, and for baseline to Month 12, percentages will only be calculated based on the number of subjects with valid data for baseline and post-baseline; subjects who are missing either assessment will not be included in the percentage calculation (numerator or denominator). Results from repeat/unscheduled visits will be included in the shift analyses, as applicable.

Summaries of all laboratory parameters will also be presented by region (North America and Europe).

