## Appendix D. Normalization of Clinical Laboratory Values

Because normal values of laboratory parameters in this study were provided from different local or central laboratories with inconsistent units and normal ranges, all numerical values will be converted to the Standard International (SI) units and normalized to a standard set of reference/normal ranges as described by Chuang-Stein (1992 and 2001). The normalization process will be performed separately for each of the laboratory parameters.

For numerical laboratory values, the normalized values will be proportional to the ratio of the widths of reference ranges and aligned with the corresponding lower limits. For example, let  $(L_s, U_s)$  denote the standard reference range, which is the Medpace normal ranges in this study. Let  $(L_A, U_A)$  represents the reference range from a central or local Laboratory  $A$ . Let  $\varphi$  denote the laboratory value provided from Laboratory  $A$ , which is needed to be normalized. The normalized value,  $\varphi_s$ , can be derived from the formula,

$$\varphi_s = L_s + \beta \times (\varphi - L_A),$$

[figure not shown]
where  $\beta = (U_s - L_s) / (U_A - L_A)$  equals the ratio of the widths of the reference ranges.

If the normalized value,  $\varphi_s$ , becomes negative, the value will be replaced by zero. If one, say the lower, of the limits of a reference range is missing then the missing limit will be imputed according to the ratio of the limits from one of the closest reference ranges provided in this study. For example, let  $L_M$  denote the missing lower limits from Laboratory  $M$ . Its corresponding higher limit,  $U_M$ , is found to be closest to the upper limit,  $U_C$  from Laboratory  $C$  among all the reference upper limits in the study. Then,  $L_M$  will be imputed by the formula,

$$L_M = L_C \times (U_M / U_C),$$

where  $L_C$  denotes the lower limit from Laboratory  $C$ . For cases where only the upper limits are missing (i.e., the lower ones are non-missing), same imputation process will be performed. For cases where both limits of a reference range are missing, the missing upper and lower limits will be imputed by the largest upper and lowest lower limit among all the observed reference ranges, respectively.

Signature Page for RAD-CLIN-002892 v1.0

Approval	
	17-Sep-2021 15:59:22 GMT+0000

Approval	
	17-Sep-2021 16:22:11 GMT+0000

Approval	
	20-Sep-2021 18:16:50 GMT+0000

Signature Page for RAD-CLIN-002892 v1.0

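### The hypercalcemia analysis labels sMTS minus SC a risk reduction, so excess risk on sMTS is reported as a positive reduction; its ULN offsets and the period it covers also need correcting

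*SAP*

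**What the plan says.** SAP 1.2.5.2 makes this a named safety assessment: "the presence of hypercalcemia and of hypercalciuria based on laboratory values will be assessed". SAP 4.6.5.2 sets three cutoffs for albumin-corrected serum calcium: (a) ULN, (b) ULN plus 0.3 mg/dL (0.08 mmol/L) and (c) ULN plus 1.0 mg/dL (0.25 mmol/L). For each cutoff it gives per-arm percentages with Wilson intervals. For the whole treatment period it adds three between-arm results:

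- A test: "The treatment groups will be compared using the chi-square test".
- An absolute measure: "The risk reduction between the treatment groups (calculated as Abaloparatide-sMTS" minus the SC rate, with a Newcombe interval.
- A relative measure: "The relative risk reduction between the treatment groups (calculated as (Abaloparatide-sMTS" minus SC, divided by SC, with an interval by Wald's method.

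The parent section, SAP 4.6.5, explains why values are rescaled: "Normal values of laboratory parameters in this study were provided by different local and central laboratories with inconsistent units and normal ranges". The central laboratory was also replaced midway. The default for tables is stated there: "Summaries of laboratory data will be presented using normalized laboratory values". Under Appendix D, "the normalized values will be proportional to the ratio of the widths of reference ranges and aligned with the corresponding lower limits", with the second central laboratory's ranges as the reference.

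Footnote 10 of the schedule, identical in both documents, reports corrected calcium at Screening, Day 1 and Months 1, 3, 6 and 9. The chemistry panel is also drawn at Month 12 (protocol Table 1 and 6.2.7.14), and protocol Table 2 lists albumin and total calcium in that panel.

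**The concern.** A reduction in an adverse outcome normally means control minus test, so that a positive figure favours the test product. Here the subtraction runs the other way under the same name, and no sign convention is given. SAP 4.6 plans no formal safety testing unless otherwise specified, and this is the only between-arm test in that section. The labelled estimates are therefore likely to be carried into a report or a label discussion, where the name could be read without the formula.

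The other two matters concern what is counted. An offset of 0.3 or 1.0 mg/dL above ULN is an absolute amount, and rescaling by range width does not preserve it. A rate described as covering the entire treatment period should not rest on samples that, as scheduled, stop at three-quarters of it.

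**Working it through.** The documents give no planned hypercalcemia rate, so there is no figure of the plan's own to reproduce. All counts and event chances below are assumptions. The 237 per arm is the planned allocation (SAP 3.1).

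**1. Sign of the labelled statistics.** Assume 24/237 on sMTS and 12/237 on SC.

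- Rates: 24/237 = 0.1013 (Wilson 0.0690 to 0.1463); 12/237 = 0.0506 (0.0292 to 0.0864).
- SAP 'risk reduction' = 0.1013 − 0.0506 = +0.0506 from unrounded rates; Newcombe 95% CI 0.0025 to 0.1005, that is +5.1 points (0.2 to 10.0).
- SAP 'relative risk reduction' = (24 − 12)/12 = +100%.
- Chi-square (uncorrected) = 4.33, p = 0.037, with no sign.

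Risk has doubled, yet both labelled figures are positive reductions. With the arms swapped, a true halving is reported as −5.1 points and −50%. The sign is reversed for every pair of unequal rates.

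The relative interval depends on a choice that the SAP leaves open. SE(log RR) = sqrt(1/24 − 1/237 + 1/12 − 1/237) = 0.3414.

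- Log-scale Wald: exp(log 2 ± 1.96 × 0.3414) = 1.024 to 3.905, so +2% to +291%.
- Linear Wald: 1.00 ± 1.96 × 2.00 × 0.3414, so −34% to +234%.

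**2. Offsets under Appendix D.** The map is φ_S = L_S + β(φ − L_A), with β = (U_S − L_S)/(U_A − L_A). Put in a value d above the source laboratory's limit, φ = U_A + d:

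φ_S = L_S + β(U_A − L_A) + βd = L_S + (U_S − L_S) + βd = U_S + βd.

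The ULN maps to the ULN, so cutoff (a) is unchanged. An offset d becomes βd, so a sample meets cutoff (b) or (c) only at a raw excess of d/β:

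| Assumed β | Raw excess for (b), mg/dL | Raw excess for (c), mg/dL |
|---|---|---|
| 0.9 | 0.3/0.9 = 0.33 | 1.0/0.9 = 1.11 |
| 1.0 | 0.30 | 1.00 |
| 1.1 | 0.3/1.1 = 0.27 | 1.0/1.1 = 0.91 |

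The ranges are not in the documents, so the true β is unknown.

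**3. Period covered.** One month is 30 days. The last scheduled corrected calcium is at day 9 × 30 = 270 of 360, which leaves 360 − 270 = 90 days (25%). Scheduled corrected values after Day 1 are Month 1 predose, Month 1 at 4 hours, and Months 3, 6 and 9: five, or six with Month 12. If each value had the same independent event chance p, the overall rate would go from 1 − (1 − p)^5 to 1 − (1 − p)^6:

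- p = 0.5%: 2.5% to 3.0%.
- p = 2%: 9.6% to 11.4%.

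It would not change if Month 12 events occurred only in subjects already counted.

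**4. Text that disagrees with itself.** Cutoff (c) is ≥ in mg/dL but > in mmol/L. The protocol's Month 9 visit list (6.2.7.11) names serum albumin only, while the schedule and footnote 10 require calcium and albumin.

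**The case against.** The label is a naming fault and not an analytic one. Both formulas are printed, per-arm rates stand beside them, and no decision rule uses these statistics. That is correct and limits the weight of the point, but the names still state the opposite of the result.

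On scale, a reader might infer that the SAP is silent. It is not: the parent section makes normalized values the default. The fault is that this default alters absolute offsets and no exemption is made. A reader might also infer that local laboratories distort on-treatment events. Footnote 7 of the schedule allows local testing only at Screening, so on-treatment samples come from the two central laboratories, and only those from the replaced one can be rescaled.

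A stronger reading is that calcium and albumin are each normalized before being combined, which could move cutoff (a) as well. The order of steps is not stated, so this cannot be excluded, but the documents do not support it. Protocol 4.7.1 gives corrected calcium its own normal range, and Appendix D says: "The normalization process will be performed separately for each of the laboratory parameters". Any shift by that route would rest on invented ranges.

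On coverage, it would be too strong to say that no corrected calcium exists after Month 9. Protocol 4.7.1 calls for redraws after elevated values, and some may fall later. They are triggered samples, however, and not systematic coverage. Month 12 total calcium also enters the shift tables (SAP 4.6.5) and the Appendix C criteria, and hypercalcemia is an adverse event of special interest (SAP 4.6.2). The five-versus-six comparison probably overstates the gain, because one of the five is a 4-hour postdose sample while Month 12 blood is drawn predose.

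**Conclusion.** The concern holds in three parts of unequal weight.

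- **Label.** Wrong as written for both the absolute and the relative measure. In the assumed example a doubled risk is reported as +5.1 points and +100% reduction. Whether the relative interval excludes zero depends on the Wald scale, so a reader should not infer that the planned table would show a clear relative effect on these counts.
- **Offsets.** Cutoffs (b) and (c) do not keep their stated meaning for samples from the replaced central laboratory unless β = 1. Size and direction are unknown. A reader might infer bias between arms, but rescaling depends on the laboratory and not on treatment, and none is shown.
- **Coverage.** The rate for the entire treatment period has no scheduled corrected value in its last 90 days. The assumed event chances show a modest possible change and no differential effect.

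All of this concerns one safety analysis. The primary non-inferiority conclusion on lumbar spine BMD is not affected.

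**What to change.** 1. Rename the statistics 'risk difference' and 'relative risk difference' (sMTS minus SC), or keep the names and reverse the subtraction. State the scale of the Wald interval.
2. State that hypercalcemia is classified on original corrected-calcium values against the reporting laboratory's own ULN, and exempt this analysis from normalization. Merely confirming normalized values would remove doubt about the scale but would not restore the stated offsets.
3. Write down the albumin-correction formula, which neither document gives. Derive Month 12 corrected calcium with the same correction used at the other visits, include it in the by-visit and overall rates, and record the change from footnote 10. Otherwise, label the rate 'scheduled samples through Month 9'.
4. Reconcile the two operators of cutoff (c), and the Month 9 visit list with the schedule and footnote 10. No threshold is proposed here.

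The cost is SAP wording and programming. SAP 4.6.5 already keeps original results in the laboratory listings, and Month 12 calcium and albumin are already drawn. SAP Section 1 provides for recording significant changes from the planned analysis in Section 9.8 of the study report.

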#### **4.6.5.3. Hypercalciuria**

The number (%) of subjects with at least one occurrence of hypercalciuria (urine calcium/creatinine ratio  $>$  0.4 mg/mg ( $>$  1.131 mmol/mmol)) at Baseline (Day 1), Month 3, and overall will be summarized by treatment group and visit. A 95% CI for the percentage based on Wilson's Score method will be calculated for each treatment group at each visit and overall. This analysis will be repeated for subjects with at least one occurrence of urine calcium/creatinine ratio  $>$  0.3 mg/mg ( $>$  0.848 mmol/mmol).

To evaluate the relationship between age and hypercalciuria, the number (%) of subjects with at least one occurrence of hypercalciuria at each visit and overall will be summarized by treatment group and age group (< 65, 65 - < 75, and  $\geq$  75 years).

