4.7.2. Treatment Algorithm in Subjects who Develop Hypercalciuria

For a urine calcium:creatinine ratio > 0.4 mg/mg, corresponding to > 1.131 mmol/mmol, check the subject's predose serum calcium (albumin-corrected) and apply the algorithm outlined in Section 4.7.1 if calcium is elevated.

If the calcium:creatinine ratio is > 0.4 mg/mg and serum calcium is normal:

- Discontinue calcium and vitamin D supplements and recheck urine calcium:creatinine ratio after 7 days.
 - If the urine calcium:creatinine ratio continues to be > 0.4 mg/mg in the presence of normal serum calcium, the subject may continue in the study under medical supervision (and without receiving additional calcium and vitamin D supplements).
 - If the urine calcium:creatinine ratio returns to normal, the subject may restart calcium and vitamin D supplements and continue in the study.
- If the subject restarts the calcium and vitamin D supplements and hypercalciuria returns, calcium and vitamin D supplementation should be terminated. The subject may continue in the study under medical supervision.

Therefore, subjects with hypercalciuria will not be discontinued from the study in the absence of hypercalcemia except at the discretion of the Investigator

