- 9. X-ray results will be evaluated by a qualified evaluator at the site, with prevalent fractures assessed using the Genant-semiquantitative scoring method.
- 10. Serum calcium and albumin will be measured predose from the standard chemistry panel on Screening, Day 1, Month 1 and Month 6 and from a separate blood draw predose at Month 3 and Month 9 and at 4 hours postdose at Month 1. Albumin corrected serum calcium will be reported using the serum calcium and albumin results on the following visits: Screening, Day 1, Month 1, Month 3, Month 6 and Month 9.
- 11. A 24-hour urine collection will be collected at Day 1 and Month 3 and will be used for urinary calcium and urinary creatinine measurements. Subjects will discard the 1st void and begin a 24-hour urine collection on the day prior to the study site visit.
- 12. Spine radiographs at screening will be assessed locally. If the subject reports that a fracture has occurred, remind the subject to bring X-rays and any medical reports of the fracture to the next study site visit. Documentation must be obtained on all new fractures that occur during the study. This documentation should be maintained in the source documents.
- 13. Each DXA for a given subject should be performed on the same machine, and if available, preferably by the same technician and will be assessed by a central imaging laboratory. For screening purposes, DXA scans of the lumbar spine, total hip, and femoral neck taken up to 35 days prior to the beginning of the Screening Period may be used to enroll a subject in the study if the BMD T-score criteria in Section 6.2.5 are met.
- 14. Samples for ADA will be drawn prior to treatment on Day 1, Day 14, Month 1, Month 3, Month 6, Month 9, Month 12/EOT, and 1 month following the last dose of study drug. All subjects who remain antibody positive will continue to be followed for ADA testing every 6 months until the result is negative.

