8. Any subject with a TSH value outside of the normal range may have T3 and free T4 tested, with results within the normal range in order to be enrolled.
9. X-ray results will be evaluated by a qualified evaluator at the site, with prevalent fractures assessed using the Genant-semiquantitative scoring method.
10. Serum calcium and albumin will be measured predose from the standard chemistry panel on Screening, Day 1, Month 1 and Month 6 and from a separate blood draw predose at Month 3 and Month 9 and at 4 hours postdose at Month 1. Albumin corrected serum calcium will be reported using the serum calcium and albumin results on the following visits: Screening, Day 1, Month 1, Month 3, Month 6 and Month 9.
11. A 24-hour urine collection will be collected at Day 1 and Month 3 and will be used for urinary calcium and urinary creatinine measurements. Subjects will discard the 1st void and begin a 24-hour urine collection on the day prior to the study site visit.
12. Spine radiographs at screening will be assessed locally. If the subject reports that a fracture has occurred, remind the subject to bring X-rays and any medical reports of the fracture to the next study site visit. Documentation must be obtained on all new fractures that occur during the study. This documentation should be maintained in the source documents.
13. Each DXA for a given subject should be performed on the same machine, and if available, preferably by the same technician and will be assessed by a central imaging laboratory. For screening purposes, DXA scans of the lumbar spine, total hip, and femoral neck taken up to 35 days prior to the beginning of the Screening Period may be used to enroll a subject in the study if the BMD T-score criteria in protocol Section **Error! Reference source not found.** are met.
14. Samples for ADA will be drawn prior to treatment on Day 1, Day 14, Month 1, Month 3, Month 6, Month 9, Month 12/EOT, and 1 month following the last dose of study drug. All subjects who remain antibody positive will continue to be followed for ADA testing every 6 months until the result is negative.

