#### **4.6.5.4. Creatinine Clearance and Calcium Excretion**

From the 24-hour urine collection at Day 1 and Month 3, urine sample values will be adjusted for the time period for the sample collection to derive the urine result that is standardized for a 24-hour period. The 24-hour urine results will be summarized descriptively by treatment group and visit. If the end of the collection time of the 24-hour urine is on the same day as the first dose date or within 24 hours from the time of first dose, then the 24-hour urine sample will be considered as a Day 1 sample and will be treated as the baseline sample. Otherwise, the 24-hour urine data will be considered as a post-Day 1 (i.e. post-baseline) sample.

The parameters to be summarized include:

- Urine calcium: creatinine ratio
- 24-hour urine calcium excretion (calcium concentration  $\times$  24-hour urine volume)
- 24-hour urine creatinine excretion (creatinine concentration  $\times$  24-hour urine volume)
- Creatinine clearance (CCr) calculated in two ways:
  - a. Based on 24-hour urine collection
  - b. Based on serum creatinine, calculated using the Cockcroft-Gault estimate, CCr:

$$CCr \text{ (mL/min)} = \{[(140 - age) \times weight \times 1.23] \div SCr\} \times F$$

where:

- *age* = in years
- *weight* = in kilograms
- *F* (constant) = 0.85 for females
- *SCr* = serum creatinine in  $\mu$ mol/L.

The following categories of renal function will be defined:

	Cockcroft-Gault Estimated Serum Creatinine Clearance
Normal	$\geq 90 \text{ mL/min} (\geq 1.5 \text{ mL/s})$
Mild	$\geq 60 \text{ mL/min to } < 90 \text{ mL/min} (\geq 1.0 \text{ mL/s to } < 1.5 \text{ mL/s})$
Moderate	$\geq 30 \text{ mL/min to } < 60 \text{ mL/min} (\geq 0.5 \text{ mL/s to } < 1.0 \text{ mL/s})$
Severe	$\geq 15 \text{ mL/min to } < 30 \text{ mL/min} (\geq 0.25 \text{ mL/s to } < 0.5 \text{ mL/s})$

The number (%) of subjects in each renal function category at each visit and overall (across all visits) will be presented by treatment group. A similar summary table will be presented by treatment group and age group (< 65, 65 - < 75, and  $\geq 75$  years).

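### The 'overall' hypercalciuria rate in SAP 4.6.5.3 is undefined; read plainly it counts women above the cut-off before any drug, and no laboratory-based new-onset rate is planned

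*SAP*

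**What the plan says.** SAP 4.6.5.3 defines hypercalciuria as a urine calcium/creatinine ratio above 0.4 mg/mg and repeats the summary at 0.3 mg/mg. Women with at least one such value "at Baseline (Day 1), Month 3, and overall will be summarized by treatment group and visit". Each percentage, including 'overall', gets a Wilson 95% interval per arm, and an age-group table again reports each visit and 'overall'. The section does not limit 'overall' to post-baseline samples and does not remove women already above the cut-off at baseline.

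The schedule has two collections: "A 24-hour urine collection will be collected at Day 1 and Month 3 and will be used for urinary calcium and urinary creatinine measurements" (SAP Table 1, note 11). On timing, the protocol's Table 1 adds: "Subjects will discard the 1st void and begin a 24-hour urine collection on the day prior to the study site visit". SAP 4.6.5.4 says that a collection ending on the day of the first dose, or within 24 hours of it, "will be considered as a Day 1 sample and will be treated as the baseline sample".

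Neighbouring sections are more specific. For hypercalcemia (SAP 4.6.5.2), the count is of values "above the cutoff level at each visit, timepoint, and overall (entire treatment period"). For potentially clinically significant (PCS) laboratory values (SAP 4.6.5.1), "subjects with post-baseline PCS values who did not have PCS values at baseline will be presented", and "the denominator will be based on the number of subjects who had no PCS values at baseline and had at least one post-baseline assessment".

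**The concern.** SAP 1.2.5.2 names laboratory-based hypercalciuria as a safety assessment, and Protocol 1.1.2.2.1 lists hypercalciuria among the common adverse reactions to abaloparatide-SC. A reader will take the 'overall' row as the share of women who became hypercalciuric on each product. If Day 1 counts toward it, the row mixes a pre-drug condition with an on-drug effect. That carries into the overall rate in each arm, its Wilson interval and the age-group figures. Anyone setting patch beside injection on that row would see a smaller relative difference than the one the drugs produced, if the baseline rates are alike.

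**Working it through.** **Step 1. Which samples can feed 'overall'.** The scheduled ones are Day 1 and Month 3. Beyond these, Protocol 4.7.2 sets a 7-day recheck, which starts from a high value: "For a urine calcium:creatinine ratio > 0.4 mg/mg, corresponding to > 1.131 mmol/mmol". SAP 4.6.5.4 also lets a late 'Day 1' collection count as post-baseline. SAP 4.6.5.3 does not say whether rechecks count.

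**Step 2. The plain reading.** Baseline is one of the listed visits and 'overall' follows without a limit, so it covers Day 1 or Month 3, plus any rechecks. If Day 1 were left out, 'overall' would repeat the Month 3 row apart from a few unscheduled or late samples.

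**Step 3. Can baseline-positive women be in the study?** Yes. Inclusion criterion 5 requires normal serum calcium, but no criterion in Protocol 4.1 or 4.2 addresses urine calcium, and none is scheduled before the Day 1 collection.

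**Step 4. Does another table give a new-onset rate?**
- The Month 3 row includes women already positive at Day 1.
- The PCS rule covers Appendix C parameters only. Its urine entries are glucose, protein and blood.
- The hypercalciuria adverse event of special interest (SAP 4.6.2) is built from reported adverse events. Protocol 7.1.1 makes a laboratory value an adverse event only if it needs intervention or is judged clinically significant.

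So no laboratory-based new-onset rate is planned.

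**Step 5. Effect on the numbers.** The plan states no hypercalciuria rate, so there is nothing to reproduce, and every rate below is an assumption. Let b be the baseline rate (equal in both arms) and q the Month 3 rate among women negative at baseline.

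- Overall rate = b + (1-b)q.
- Overall risk difference = [b + (1-b)q_patch] - [b + (1-b)q_injection] = (1-b)(q_patch - q_injection).
- Overall ratio = [b + (1-b)q_patch] / [b + (1-b)q_injection], which is nearer 1 than q_patch/q_injection whenever b > 0.

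With q = 10% (patch) and 20% (injection), the new-onset difference is -10.0 points and the ratio 0.50:

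| b | Overall, patch | Overall, injection | Difference (points) | Ratio |
|---|---|---|---|---|
| 2% | 11.8% | 21.6% | -9.8 | 0.55 |
| 5% | 14.5% | 24.0% | -9.5 | 0.60 |
| 10% | 19.0% | 28.0% | -9.0 | 0.68 |
| 20% | 28.0% | 36.0% | -8.0 | 0.78 |

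With q = 6% and 12% (ratio again 0.50), the overall ratio at the same values of b is 0.57, 0.65, 0.74 and 0.84.

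**Step 6. Comparison with the Month 3 row.** Let r be the chance that a baseline-positive woman is still positive at Month 3. The Month 3 rate is (1-b)q + br. Take b = 10% and q = 10% and 20%; the overall ratio is 0.68 throughout. The last column is the share of patch-arm overall cases counted only because of Day 1, b(1-r)/overall:

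| Persistence | Month 3 rates | Month 3 ratio | Day 1-only share |
|---|---|---|---|
| Independent (r = q) | 10.0% and 20.0% | 0.50 | 0.10 × 0.90 / 0.19 = 47% |
| r = 50% | 14.0% and 23.0% | 0.61 | 0.10 × 0.50 / 0.19 = 26% |
| r = 100% | 19.0% and 28.0% | 0.68 | 0% |

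The gap between the two rows depends on persistence and vanishes if every baseline case persists. In that case the Month 3 row is as far from the new-onset ratio as the overall row is.

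**The case against.** Several points on the other side stand.

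- A reader might infer that the SAP explicitly pools Day 1 with Month 3. It does not; 'overall' is undefined. The hypercalcemia section just before restricts it to the treatment period, and SAP 4.6.5.4 and 4.6.6 say so when they mean all visits. A post-baseline reading is possible, and rechecks and late collections would keep it from being an exact copy of Month 3. Pooling is the plain reading, and the text needs a definition either way.
- A reader might infer that no on-treatment rate is reported. The Month 3 row is reported by arm with its own interval, at both cut-offs, beside the Baseline row. It is a prevalence, though, and not new onset.
- A reader might infer that a planned treatment comparison is biased. None is planned: SAP 4.6.5.3 gives per-arm intervals only, and SAP 4.6 makes safety descriptive unless otherwise specified. The differences and ratios above are calculated for this review.
- The absolute shift is modest: at b = 10% it is 1 point in 10. The entry rules on serum calcium, parathyroid hormone and urinary stones may also keep b low.
- Dilution holds in expectation. At b = 10% and 237 per arm, the standard error of the baseline difference is √(2 × 0.10 × 0.90 / 237) = 2.8 points, so chance imbalance could move the contrast either way.
- The PCS rule does not formally cover urine calcium, and the hypercalcemia section does not remove baseline-positive women either. They show that the SAP has the wording available; they do not put it in conflict with itself.
- Under SAP 4.6.5.4 a few 'Day 1' samples may end after the first dose, so not every baseline case is strictly pre-drug.

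**Conclusion.** The point holds as a matter of definition and of a missing row. Followed as it plainly reads, SAP 4.6.5.3 produces an overall rate, a Wilson interval and an age-group table that are not on-treatment incidence, and nothing else in the plan supplies laboratory-based new onset. With equal baseline rates the overall risk difference is (1-b) times the new-onset one, and the ratio moves toward 1. How far is unknown: the assumed range of b from 2% to 20% takes a ratio of 0.50 to between 0.55 and 0.84 across the two sets of new-onset rates. The documents do not support the stronger reading that a planned between-arm result is compromised, and no efficacy result is touched. This is a cheap improvement to the safety tables.

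**What to change.** In SAP 4.6.5.3, for both cut-offs and for the age-group table:

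1. Define 'overall' as any post-baseline urine collection.
2. Add a row with the number and percentage of women with new-onset hypercalciuria: those not above the cut-off at baseline, with at least one post-baseline urine, who exceed it afterwards. This is the denominator rule of SAP 4.6.5.1. Item 1 alone is not enough, because women positive at Day 1 can still be post-baseline cases at Month 3 or at a recheck that their Day 1 value triggered.
3. Keep the Baseline row as description.

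The cost is a short change of SAP wording, one changed filter and one added row, with no new data. The new-onset denominator is slightly smaller than the full Safety population, so its interval will be a little wider than one based on all women.
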